### 9.11 Early Termination Visit

For any subject who is withdrawn before completing all study visits, the Investigator will ensure that the following steps are taken at an early termination (ET) visit:

- Conduct an ET visit performing study activities listed under Visit 9 ([Section 9.10](#)) no later than 14 days after withdrawal or discontinuation from the study
- If the subject fails to attend a scheduled ET visit, site staff will make at least 2 attempts to contact the subject via telephone and 2 attempts via written communications delivered by courier (delivery should be confirmed and documented). If the subject does not respond to any of these attempts at communication, he or she will be considered lost to follow-up
- Complete all appropriate eCRF pages, providing the date of and explanation for the subject's withdrawal/discontinuation
- When indicated, the Investigator should arrange for appropriate follow-up medical care for the subjects

**If a subject discontinues the study prematurely, it is very important for site personnel to encourage subjects to visit the site at Week 26 ( $\pm$  4 weeks) (and Week 12  $\pm$  1 week, if applicable) for a blood sample to be obtained for AIA and HbA1c measurements.**

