6.4 Exploratory Endpoints

- Retrospective CGM hypoglycemia rate
- Time in hypoglycemia and hyperglycemia event based on CGM data
- Relationship between plasma concentrations of insulin glargine, M1, and M2, and AIA titers

8) Diabetes Disease Duration

The duration of diabetes is defined as the number of years from the date of original diagnosis of Type 1 Diabetes Mellitus to the date of randomization (presented in full years):

$$(\text{date of randomization} - \text{date of Type 1 diagnosis} + 1)/365.25$$

If the date of Type1 Diabetes Mellitus diagnosis is partially missing, then the following imputation rules will be applied:

- Missing day, but month and year are present: the day will be imputed as the 1st of the month.
- Missing day and month but year is present: the day and month will be imputed as July 1, or date of consent, whichever is earlier.
- Date completely missing: no imputation will be done, and diabetes disease duration will also be missing.

9) QD Compliance Dosing Regimen

QD Compliance is where the answer to the question "Was the subject compliant with QD dosing since the previous visit?" is Yes on all Average Daily Dose of Study Drug CRF pages. If a subject does not answer Yes then they are marked as No in all associated outputs.

10) Double Average Daily Dose

Double Average Daily Dose is defined as having at least double the average daily dose compared to the first average daily dose after randomization at any subsequent average daily dose assessment.

11) Eligibility-Related Important Protocol Deviation (ERIPD)

Eligibility-related important protocol deviations are important protocol deviations coded to the Inclusion Criteria or Exclusion Criteria categories or Other category with deviation that has description "Inadequate source documentation that is required to support eligibility assessment". Site POL008 has been placed in this Other category and is used in this derivation as the deviation relates to documentation of eligibility. (refer to Appendix 4 Immunogenic- and Efficacy-Interfering Important Protocol Deviations for details).

12) End of Treatment visit

The End of Treatment visit (EOT) is defined as the scheduled visit labelled in data as 'Visit 9 Week 26/ End of Study'. This includes any subject who discontinues from treatment before visit Week 26 who has scheduled Visit 9 procedures performed at a EOT visit.

13) Exposure

- Duration of therapy (presented in weeks with one decimal place)

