11.6.1 Primary Endpoint

11.6.1.1 Incidence of Treatment-Induced Anti-Insulin Antibodies

Incidence of treatment-induced AIA is defined as subjects develop newly confirmed positive AIA or have important (4-fold) increase in AIA titer up to visit Week 26. The objective of the primary immunogenicity analysis will be to evaluate equivalence of Gan & Lee Insulin Glargine Injection to Lantus® by comparing the limits of the 90% confidence interval (CI) of country-adjusted difference in proportions of treatment-induced AIA development to the specified margins (-margin, +margin) where the margin is dependent on the unadjusted treatment-induced AIA rate in Lantus® and is defined in Section 5.1, Table 3.

The estimand of interest is the country-adjusted difference in treatment-induced AIA rates regardless if all subjects tolerate or adhere to study treatment or receive other insulin treatments. Intercurrent events will be handled according to the treatment policy strategy. Treatment Policy strategy is defined as the strategy that considers "The occurrence of the intercurrent event is irrelevant: the value for the variable of interest is used regardless of whether or not the intercurrent event occurs" (See ICH E9 R1 addendum). All AIA data collected, scheduled and unscheduled, will be considered for the analysis, even if collected after the occurrence of intercurrent events of (1) discontinuing study treatment, (2) returning to initial treatment and/or (3) initiating a new treatment.

Any treatment-induced AIA after baseline and up to visit Week 26 will have the subject count as treatment-induced AIA for the primary endpoint. The visit window (defined in Section 7.1) will only be limited to include assessment within 210 days from the first dose.

Missing data will be handled as described in Section 11.6.1.2. The SS will be used for the primary analysis.

The number and percentage of subjects in each treatment group who develop treatment-induced AIA as defined in Section 7.2 after baseline and up to visit Week 26 (upper limit of the visit window) will be evaluated using a logistic regression model adjusted by country (CNTRY) estimating the country-adjusted difference in proportions along with the corresponding 90% confidence interval (CI).

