11.7 Efficacy Analyses

11.7.1 Key Secondary Endpoint

An overview of planned analyses for the key secondary endpoint of change from baseline in HbA1c, including sensitivity analyses, is provided in Table 5 below.

Table 5: Overview of key secondary endpoint analyses

Analysis	Population used	Analysis Details	Section reference
1. Main analysis	Full analysis set	Treatment Policy Estimand - ANCOVA using MI under the assumption of MNAR; this analysis uses unscheduled HbA1c results from discontinued subjects to impute missing in each treatment arm.	Section 11.7.1.1 Change from Baseline in HbA1c at 26 weeks
2. Sensitivity analysis	Per protocol analysis set	ANCOVA using MI under the assumption of MNAR; this analysis uses the same approach for imputation as the main analysis. Used to assess the robustness of main analysis to important deviations from the protocol.	Section 11.7.1.3 Sensitivity Analyses - PPS
3. Sensitivity analysis	Full analysis set of completers	ANCOVA without imputation. This analysis is used to assess the robustness of main analysis to subjects lost to follow-up.	Section 11.7.1.3 Sensitivity Analyses - FAS completers

For subjects who discontinue from treatment before visit Week 26 or who have no HbA1c measurement at visit Week 26, HbA1c will be assigned to the scheduled time point if they fall within the upper limit of visit window defined in Section 7.1 (that is, for study day ≤ 210).

Submissions to Food and Drug Administration (FDA) and European Medicines Agency (EMA) require different methods for efficacy HbA1c evaluation.

For FDA submission, equivalence in change from baseline in HbA1c between Gan & Lee Insulin Glargine Injection (μ_1) and Lantus® (μ_2) will be tested using the two one-sided tests (TOST) approach proposed in Schuirmann (1987) (7) with the following null hypothesis:

$$H_0: (\mu_1 - \mu_2) \leq -0.4 \text{ or } (\mu_1 - \mu_2) \geq 0.4$$

Against the alternative hypothesis of:

$$H_1: -0.4 < (\mu_1 - \mu_2) < 0.4$$

with $\alpha=0.05$.

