The 90% CI will be estimated using a pattern mixture model that uses multiple imputation (MI) analyzed using Analysis of Covariance (ANCOVA) with treatment and stratification factor of country (CNTRY) included as fixed effects and baseline HbA1c included as a covariate. Separately in each treatment group, the imputation will use outcomes in subjects who discontinued treatment prior to Week 26 but returned to provide a visit Week 26 HbA1c sample to impute outcomes in subjects without actual visit Week 26 recorded results under the MNAR assumption. Limits of the imputed value will use the minimum of HbA1c values and the maximum of all HbA1c values assessed, and rounded to the nearest integer. These values are found in the database to be minimum as 5 and the maximum as 13. No imputation will be performed for missing baseline HbA1c. Equivalence will be assessed based on the 90% CI; no p-values will be computed. Change from baseline in HbA1c between Gan & Lee Insulin Glargine Injection and Lantus® will be considered equivalent if the 90% CI is within the margins (-0.4%, 0.4%).

For EMA submission, non-inferiority in change from baseline in HbA1c between Gan & Lee Insulin Glargine Injection and Lantus® will be tested using the following null hypothesis:

$$H_0: (\mu_1 - \mu_2) \geq 0.4$$

Against the alternative hypothesis of:

$$H_1: (\mu_1 - \mu_2) < 0.4$$

with a 1-sided $\alpha=0.025$.

In addition, the same non-inferiority test with a margin of 0.3% will be performed.

The 95% CI will be estimated using a pattern mixture model that uses MI analyzed using ANCOVA with treatment and stratification factor of country (CNTRY) included as fixed effects and baseline HbA1c included as a covariate. Separately in each treatment group, the imputation will use outcomes in subjects who discontinued treatment prior to Week 26 but returned to provide a visit Week 26 HbA1c sample (labeled as the unscheduled) to impute outcomes in subjects without actual visit Week 26 recorded results under the MNAR assumption. No imputation will be performed for missing baseline HbA1c.

Analysis of HbA1c will follow a hierarchical testing strategy: first, non-inferiority will be tested using a margin of 0.4% and only if this test is significant, then non-inferiority will be tested using a margin of 0.3%.

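### The HbA1c visit rule, as shown, sets no earliest day, so an early-termination sample can be read as the Week 26 value, with a bias of uncertain sign and size.

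*SAP*

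**What the plan says.** The key secondary endpoint is the change in HbA1c at Week 26, under a treatment policy estimand. SAP 11.7.1 covers subjects who stop treatment before Week 26 or have no Week 26 measurement. For them it states that "HbA1c will be assigned to the scheduled time point if they fall within the upper limit of visit window". The sentence refers to Section 7.1 for that limit and gives it as day 210 of the study.

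Four other places bear on which values that lets in.

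- Protocol 9.11 tells sites to "Conduct an ET visit performing study activities listed under Visit 9", and to do so "no later than 14 days after withdrawal or discontinuation from the study". Protocol 9.10 lists HbA1c among the Visit 9 tests.
- SAP definition 12 (End of Treatment visit) identifies that visit by its Week 26 / End of Study label and adds: "This includes any subject who discontinues from treatment before visit Week 26 who has scheduled Visit 9 procedures performed at a EOT visit".
- SAP 11.7.1 takes discontinuers who came back with a Week 26 sample as donors, separately by arm, "to impute outcomes in subjects without actual visit Week 26 recorded results under the MNAR assumption".
- Protocol 9.11 also asks sites to "encourage subjects to visit the site at Week 26", within ± 4 weeks, for AIA and HbA1c samples.

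**The concern.** Taken together, these texts allow an early on-treatment value to pass as a Week 26 outcome. A subject who withdraws at Week 6 has a termination visit by about day 56 (6 × 7 + 14). The visit carries the Visit 9 label, includes HbA1c and satisfies the day 210 limit.

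Two things could follow. The subject counts as observed and is never imputed, which amounts to carrying an early value forward inside an analysis meant to estimate the Week 26 outcome whatever happened to treatment. The value might also be taken as coming from a discontinuer with a Week 26 result, and so feed the imputation of others. Both conflict with reserving imputation for subjects who have no *actual* Week 26 result.

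The endpoint supports an equivalence claim for FDA and a non-inferiority claim for EMA. In either test, an error that makes the arms look more alike helps the claim. SAP 5.1 reports more early discontinuation than expected, so such samples are likely to exist, although no percentage is given.

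**Working it through.** **Plan's own figure.** No power or sample size is stated for HbA1c. The stated power is for the AIA endpoint: about 85% with 275 per arm, rate 30% and margin 12%. SE = √(2 × 0.3 × 0.7 / 275) = 0.0391, and power = 2Φ(0.12/0.0391 − 1.645) − 1 = 84.6%, so it reproduces. It has no direct bearing here.

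**The window.** Week 26 is day 182 (26 × 7), and ± 4 weeks gives days 154 to 210. Day 210 is thus the upper end of the protocol's return window. The matching lower end, day 154 (Week 22), does not appear in the HbA1c rule.

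**What else the SAP says about windows.** For the AIA endpoint, SAP 11.6.1.1 says the Section 7.1 window "will only be limited to include assessment within 210 days from the first dose". An upper limit alone suits an antibody event counted at any time up to Week 26; it does not suit a value at Week 26. Where the SAP wants two-sided limits it writes them: definition 23 (day 182 ± 3) and the AIA completers analysis in 11.6.1.3 (Week 26 ± 4 weeks).

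**Size under similar discontinuation in both arms.** From the documents: 275 per arm, margin ± 0.4, 90% CI for equivalence, 95% CI for non-inferiority. Assumed, because the documents do not give them:

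- SD of HbA1c change: 0.8 to 1.0
- f, the share of subjects whose early value is used as Week 26
- Dₑ, the arm difference in those early values
- D_d, the difference the same subjects would have had at Week 26

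Bias = f × (Dₑ − D_d). SE = SD × √(2/275) = 0.068 (SD 0.8) or 0.085 (SD 1.0). At a true difference of 0.4, the chance of a false conclusion is Φ((0.4 − expected estimate)/SE − z), with z = 1.645 (equivalence) or 1.960 (non-inferiority).

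If discontinuers would have kept the full difference (D_d = 0.4):

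| f | Dₑ | Expected estimate | False equivalence, SD 0.8 / 1.0 | False non-inferiority, SD 0.8 / 1.0 |
|---|---|---|---|---|
| 0 | – | 0.400 | 5.0% / 5.0% | 2.5% / 2.5% |
| 5% | 0 | 0.380 | 8.8% / 7.9% | 4.8% / 4.2% |
| 10% | 0 | 0.360 | 14.5% / 12.0% | 8.5% / 6.8% |
| 10% | 0.2 | 0.380 | 8.8% / 7.9% | 4.8% / 4.2% |
| 20% | 0 | 0.320 | 31.8% / 24.0% | 21.6% / 15.3% |

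If instead discontinuers have no difference at Week 26 (D_d = 0, f = 10%), an overall difference of 0.4 means 0.4/0.9 = 0.444 in the remaining subjects.

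- Early values with no difference: bias is 0, and false equivalence stays at 5%.
- Early values with half the remaining subjects' difference (0.222): the estimate is 0.4 + 0.1 × 0.222 = 0.422, and false equivalence falls to 2.4% (SD 0.8) or 2.8% (SD 1.0).

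**Direction when discontinuation is unequal.** Assume that a quarter of each arm's change is present at the early visit, so an arm's mean change is multiplied by 1 − 0.75f. Take a reference change of −0.4 and a test change of −0.2 (true difference 0.20).

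- Early shares 10% in both arms: 0.20 × 0.925 = 0.185.
- Early shares 15% test, 5% reference: −0.1775 − (−0.385) = 0.2075.
- Same unequal shares, no true difference, both changes −0.4: −0.355 − (−0.385) = +0.03.

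The estimate can shrink, grow, or show a difference where there is none.

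**The case against.** The strongest reply is that Section 7.1, to which the rule points, is not in the supplied text. The day 210 parenthesis explains the upper limit and does not say there is no other. The rule also speaks of the scheduled time point without naming Week 26, and HbA1c is scheduled at Weeks 8, 16 and 26. The imputation text speaks of actual Week 26 results and describes the donor samples as unscheduled, which suggests that return samples were meant to be kept apart from termination samples.

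This stands in part. A reader might infer that the SAP contains no lower limit anywhere; the documents do not establish that. But the sentence concerns subjects with no Week 26 value and uses a Week 26 bound, so Week 26 is its natural meaning. If Section 7.1 does hold a lower limit, the parenthesis leaves it out and should be corrected to match.

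A reader might also infer that the rule must pull the difference toward zero, or that the false-equivalence rate is 12% to 15%. Neither is supported. The sign depends on arm-specific discontinuation and on discontinuers' true Week 26 difference, which may be small under treatment policy if they have moved to other insulins. The size rests on an SD and an early-value share that the documents do not give.

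There are partial safeguards. The FAS completers analysis (SAP 11.7.1.3) requires an actual Week 26 assessment, but it drops treatment discontinuers and so does not address the treatment policy question. The tipping-point code shifts imputed values only, so a subject counted as observed through an early sample escapes it. The MMRM is a separate analysis and does not correct the main one.

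**Conclusion.** The point holds as a defect in the stated rule. As shown, SAP 11.7.1 and definition 12 together let an HbA1c value from well before Week 22 stand for Week 26, against the section's own imputation text. The result is a bias of uncertain sign and size against the treatment policy estimand.

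The bias favours equivalence and non-inferiority if three things hold: early shares are similar in the two arms, little of the difference has developed by the early visit, and discontinuers would have kept the full difference at Week 26. Outside those conditions it can be nil or go the other way. The tabulated rates are illustrations, not estimates for this trial.

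The matter is confined to HbA1c. An upper-only window is reasonable for the primary AIA endpoint.

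**What to change.** State in SAP 11.7.1 that only HbA1c taken from study day 154 to 210 may be assigned to Week 26. Treat earlier early-termination values as missing at Week 26, impute them by the main method, and keep them out of the donor pool. Reconcile definition 12, the assignment rule and the imputation text in 11.7.1, and align all three with Section 7.1.

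SAP 11.7.1 already quotes the minimum and maximum HbA1c found in the database, so the affected subjects can be counted now, pooled over arms, and the count reported.

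The cost is one sentence and a re-derived visit flag. Slightly more subjects will be imputed, and the confidence interval may be slightly wider.

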### **12.2 Sample Size Estimation**

Enrollment is planned for 550 subjects overall (275 subjects per treatment group). The primary analysis for immunogenicity will be an equivalence test using the 2 one-sided tests (TOST) approach with  $\alpha=0.05$ . This sample size was chosen to achieve over 80% power on the equivalence test of proportion of subjects under the margins dependent on the observed treatment-induced AIA rate. For example, a sample size of 550 will provide approximately 85% power on the equivalence test of proportion of subjects with treatment-induced AIA using an event rate of 30% and a margin of 12% ([Table 4](#)). The treatment-induced AIA is defined as newly confirmed positive AIA development or important (at least a 4-fold) increase in AIA titers, after baseline and up to visit Week 26. For this sample size of 550, no drop outs are considered in the calculation. Subjects will be encouraged to come back for assessments even if they have discontinued treatment early.

The similarity margin, based on the actual observed event rate for the intended reference product, will be used for final analysis after database lock as summarized in [Table 4](#). Linear interpolation will be used for values between AIA rates in the table.

**Table 4: Similarity Margins for Actual Observed Event Rate of Proposed Biosimilar to Insulin Glargine for Various Immunogenicity Event Rates**

Treatment-induced AIA Rate for the Reference Product	Margin	Power
10%	7.9%	83%
15%	9.3%	83%
20%	10.5%	84%
25%	11.3%	84%
30%	12.0%	85%
35%	12.5%	85%
40%	12.8%	85%
45%	13.0%	85%
50%	13.1%	85%
55%	13.0%	85%
60%	12.8%	85%
65%	12.5%	85%
70%	12.0%	85%
75%	11.3%	84%
80%	10.5%	84%
85%	9.3%	83%
90%	7.9%	83%

AIA = anti-insulin antibodies.

Sample size calculations were performed using EAST Version 6.4.

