5.1 Sample Size and Power

Enrollment was planned for 550 subjects overall (275 subjects per treatment group). The primary analysis for the immunogenicity primary endpoint was to be an equivalence test for the difference in proportion of subjects who develop treatment-induced AIAAs between Gan & Lee insulin Glargine Injection and Lantus® using the 2 Wald one-sided tests (TOST) with $\alpha=0.05$ (Chow and Shao 2002 (1)). After scientific and regulatory review, the method to evaluate immunogenicity equivalence will be the 90% confidence intervals of risk difference from the logistic regression analysis (see Section 3.1). Under this newly adopted approach, no power loss is expected.

This sample size of 275 subjects per treatment group was chosen to achieve over 80% power using the TOST equivalence test for two proportions, a risk difference of zero and equivalence margins dependent on the observed treatment-induced AIA rate per Table 3 below. For example, a total sample size of 550 will provide approximately 85% power for the TOST equivalence test using a treatment-induced AIA rate of 30% and a margin of 12% (Table 3). The treatment-induced AIA is defined as newly confirmed positive AIA development or important (at least a 4-fold) increase in AIA titers, after baseline and up to visit Week 26 (see the definition of Primary Endpoint in Section 6.1 and Section 7.2). No drop outs are considered in the calculation. A larger than expected early discontinuation rate was observed as part of study monitoring activities and therefore protocol amendment 3 approved on 25-Apr-2019 included procedures to encourage subjects to return for assessments even if they had discontinued treatment early.

The appropriate similarity margin, based on the actual observed event rate for the intended reference product, will be used for final analysis after database lock as summarized in Table 3 below. The power calculation in the table was adapted for a sample size of 550 using the treatment-induced AIA rate for the reference product. Linear interpolation will be used for values between AIA rates in the table.

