11.7.1.3 Sensitivity Analyses

To evaluate the impact of important protocol deviations and missing data, sensitivity analyses will be performed using the analysis methods described for the FDA equivalence and EMA non-inferiority analyses:

- 1) PPS: Using MI approach as described for main HbA1c analysis. If in the number of subjects who discontinued treatment and return to provide an HbA1c sample at Week 26 is insufficient to perform the MI, the MI will instead be performed using data from all patients with HbA1c results at Week 26 in each treatment group under the assumption of MNAR. (Table 5, Analysis 2)
- 2) FAS Completers: This analysis will not use any imputation of missing data. Only subjects with valid baseline and visit Week 26 assessment conducted at actual visit Week 26 visit and who had treatment until visit Week 26 will be used for the analysis. (Table 5, Analysis 3)
- 3) Per Protocol Analysis Set 3 (PPS3) - Subjects with any efficacy-interfering important protocol deviations (EIIPD; as defined in Section 11.3) will be excluded from the analysis. For the subjects in the PPS3, the imputation approach as described for the main analysis will be followed. In the main analysis, subjects with efficacy-interfering important protocol deviations could falsely draw the estimated treatment difference closer. Exclusion of these subjects in this sensitivity analysis will help assess the magnitude, if any, of this effect. (Table 5, Analysis 4)

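### The main HbA1c imputation draws every missing Week 26 value from same-arm retrieved dropouts, with no minimum donor count and no visible fallback for the FAS or PPS3; precision suffers if few subjects returned.

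*SAP*

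**What the plan says.** SAP 11.7.1 describes the main HbA1c analysis (listed in SAP Table 5 as 11.7.1.1) as a pattern mixture model with multiple imputation followed by ANCOVA on the FAS. Separately by arm, "the imputation will use outcomes in subjects who discontinued treatment prior to Week 26 but returned to provide a visit Week 26 HbA1c sample". These donors supply values, under an MNAR label, for everyone without an actual Week 26 result. Table 5 describes the same approach. "Equivalence will be assessed based on the 90% CI; no p-values will be computed", and the difference "will be considered equivalent if the 90% CI is within the margins (-0.4%, 0.4"%). For EMA the upper 95% limit is compared with 0.4%, then 0.3%.

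A preceding rule in 11.7.1 assigns HbA1c results up to study day 210 to the scheduled time point, for subjects who discontinued or who have no Week 26 measurement.

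SAP 11.7.1.3 gives a fallback in the PPS item only. If the number of returning discontinuers "is insufficient to perform the MI, the MI will instead be performed using data from all patients with HbA1c results at Week 26", by arm and still labelled MNAR. No number defines insufficient. The PPS3 item refers back to the main approach without a fallback.

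Protocol 12.8.1 uses a wider pool: completers together with subjects who stopped treatment but gave a Week 26 sample, under MAR.

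SAP 5.1 reports more early discontinuation than expected and says that "protocol amendment 3 approved on 25-Apr-2019 included procedures to encourage subjects to return for assessments".

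**The concern.** An imputation model fitted to a handful of donors in each arm passes their sampling error to every imputed value in that arm. The protocol's wider pool was not exposed to this; the SAP's narrower pool is.

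Few donors is a plausible case. The procedures to encourage return came with Amendment 3 in April 2019, in a study that the protocol synopsis says started in 2017 and was expected to end in 2019. The SAP recognises the problem for a sensitivity analysis, but the visible text does not cover the analysis that carries the key secondary conclusion. With 2 or fewer donors in an arm, a regression on baseline has no residual degrees of freedom and cannot be run, and the visible text does not say what then happens.

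The recipient rule is a second matter. A subject still on treatment who lacks a Week 26 sample is imputed from off-treatment outcomes, although on-treatment completers in the same arm are the natural pattern to borrow from.

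At stake are the width and stability of the CI that decides HbA1c equivalence (FDA) and non-inferiority (EMA).

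**Working it through.** **1. The plan's own figure.** The documents state power for the primary antibody endpoint only: "a sample size of 550 will provide approximately 85% power on the equivalence test of proportion of subjects", "using an event rate of 30% and a margin of 12"%. With a true difference of 0:

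- SE = √(2 × 0.30 × 0.70 / 275) = 0.0391
- power = 2Φ(0.12/0.0391 − 1.645) − 1 = 84.6%, which reproduces the stated 85%.

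No power, SD, missing rate or donor count is stated for HbA1c, so everything below is conditional.

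**2. Inputs.**

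- From the documents: 275 per arm (Protocol 12.2); margins ±0.4% and imputed values limited to 5–13 (SAP 11.7.1).
- Borrowed from the tipping-point code (SAP 11.7.1.3), because the main-analysis code is not in the available text: 10 imputations and baseline as the predictor.
- Assumed: true difference 0; residual SD 0.8, with 1.0 as a second value; missing share 8%, 15% or 20% per arm.

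**3. Where the variance comes from.** Let f be the share who discontinued and d the donors per arm. A simple approximation to the variance of an arm mean is (1 − f)SD²/275 + f²SD²/d. With SD 0.8:

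- No missing data: SE of the difference = √(2 × 0.64/275) = 0.068.
- f = 0.15, d = 5: 0.85 × 0.64/275 = 0.00198, and 0.0225 × 0.64/5 = 0.00288. SE = √(2 × 0.00486) = 0.099.
- f = 0.20, d = 5: 0.00186 + 0.00512 = 0.00698. SE = √(2 × 0.00698) = 0.118.

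With 5 donors, the donor term already exceeds the contribution of everyone else in the arm. This approximation is too optimistic: 2Φ(0.4/SE − 1.645) − 1 gives about 98% and 92% for the two cases. It ignores that the slope and residual variance are also estimated from d − 2 = 3 degrees of freedom, that only 10 imputations are used, and that the CI width varies between trials. A full simulation is therefore needed.

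**4. Simulation.** Within each arm: Bayesian linear regression of Week 26 on baseline HbA1c fitted to the donors, bounded draws, 10 imputations, ANCOVA on treatment and baseline, Rubin's rules with t degrees of freedom. Missing subjects are counted in addition to the donors (8%, 15% and 20% of 275 is 22, 41 and 55). Chance that the 90% CI lies within ±0.4, SD 0.8:

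| Donors per arm | 8% missing | 15% missing | 20% missing |
|---|---|---|---|
| 5 | 98% | 83% | 57% |
| 12 | about 100% | 99% | 94% |
| All observed | about 100% | about 100% | about 100% |

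At 15% missing, the SE is 0.125 with 5 donors and 0.074 when all observed subjects are donors. Separate runs of the 15%, 5-donor setting gave 82% to 87%.

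**5. Second parametrisation.** Here the donors are counted within the share discontinued, SD is 0.8–1.0, and there are 200 replicates per cell (Monte Carlo error at most 3.5 points):

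| Donors per arm | 8% discontinued | 15% discontinued | 20% discontinued |
|---|---|---|---|
| 5 | 97.5–99.5% | 79–86% | 52–74% |
| 8 | at least 97% | 91–99% | 75–91% |
| 12 | at least 97% | 98–99.5% | 90–99.5% |

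With the PPS fallback applied to the main analysis and 5 returners, the chance is 98.5–100% throughout, with a median 90% half-width of 0.12–0.16.

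**6. EMA test at 0.3.** With missing counted as in step 4, 15% missing and SD 0.8, the chance of non-inferiority is about 63% with 5 donors, 75% with 8, 93% with 20 and 98% with all observed subjects.

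All runs give donors, non-returners and completers the same outcome distribution. They measure loss of precision only.

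**The case against.** **Missing text.** SAP 11.7.1.2 and the main-analysis code are not in the available text, so a fallback could be stated there. This stands: the claim is limited to the visible text.

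**The day-210 rule.** It fills some Week 26 gaps for late on-treatment samples and can add retrieved dropouts. This also stands. The window's lower limit is not visible, so neither the missing share nor the donor count can be inferred.

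**Few donors is conjecture.** The SAP is dated 27 May 2021 and cites HbA1c limits found in the database, so its authors could have known the pooled number of returners. The PPS fallback does not show that they expected a shortage in the FAS: a missed HbA1c at Visit 9 or early termination can be an important deviation (SAP Appendix 4), so donors could be scarcer in the PPS. Fair, but a known count could simply have been written into the rule.

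**A wide CI is conservative.** It makes a false equivalence claim harder and mainly costs the sponsor power. True of the precision effect, which is why this is not presented as a threat to type I error.

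**Sensitivity analyses exist.** FAS completers, MMRM and tipping-point analyses would help to reveal a result driven by few donors. None of them replaces the main CI, and the tipping-point text speaks of robustness under MAR, which is not the main model's assumption.

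A reader might infer that the equivalence claim is likely to be lost, or that the treatment difference is biased because on-treatment subjects get off-treatment values. The documents support neither. They give no rate or count that places the trial where the loss is serious. They also do not say how many on-treatment subjects lack a Week 26 value, so no bias can be sized.

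**Conclusion.** The point holds as a conditional loss of precision on the key secondary endpoint. On the visible text, the main analysis has a narrow arm-specific donor pool, no minimum count and no fallback for the FAS or PPS3, and its recipients are not limited to subjects who discontinued.

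The loss is serious at roughly 15–20% missing with about 5 to 8 or fewer donors per arm. It is small near 8% missing with 5 or more donors. With 12 or more donors it is mostly small; the exception is 20% discontinued with SD 1.0, where 12 donors give about 90%. These statements rest on the assumed SD, missing shares, zero true difference and imputation model. The mismatch for on-treatment subjects is a fault in the rule as written, but its effect is unquantified.

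**What to change.** Amend SAP 11.7.1.1 as follows.

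1. Apply the day-210 rule first.
2. Impute subjects still on treatment at Week 26 from on-treatment completers in their arm. Use retrieved dropouts only for subjects who discontinued treatment.
3. State a numeric minimum donor count per arm. Justify it by simulation at the pooled missing rate, and fix it without knowledge of results by arm. No particular number follows from the documents.
4. Below that minimum, apply to the FAS and PPS3 the fallback already written for the PPS, put the same number in the PPS item, and label the fallback MAR rather than MNAR.

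This changes SAP wording and needs a short simulation; no new data are required. The cost is inferential: under the fallback, completers largely stand in for dropouts, which may pull the arms together in an equivalence test. The tipping-point analysis must then carry the MNAR question and be described in that role.
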